- 1) **Personalized Genomic Testing for Skin Cancer – Maximizing Utility and Reach – 05/16/17**
- (v. 10)
- 2) **IRB Review History N/A**
- 3) **Objectives**

This study will have two phases, with an added usability test after Phase I and before Phase 2. Phase 1: Cognitive Interviews in Spanish.

Phase 2: Personalized Genomic Testing for Skin Cancer (PGT-SC).

The overarching goal of this study is to learn more about how to maximize the availability, comprehension and appropriate uptake of personalized genomics among different populations in New Mexico. The proposed study has been funded as an R01 by NCI for three years.

Aim I: To examine the personal utility (that is, how does personal genomic testing help the individual) of Personal Genomic Testing for Skin Cancer (PGT-SC) in terms of short-term (three months after testing) sun protection, skin screening (i.e., behaviors), communication, melanoma threat and control beliefs (i.e., putative mediators of behavior change). Guided by Protection Motivation Theory (Robberson and Rogers, 1998), **we hypothesize that behaviors and putative mediators will be higher in those who test, compared to those who decline testing or wait-list controls.**

Aim Ia. An important challenge of personal genomics involves the potential for those who receive “negative” genetic feedback to increase risky behaviors (McBride et al., 2010). To examine this potential unintended consequence of testing, we will conduct a subgroup analysis among those who receive average risk PGT-SC findings, examining sun protection at three months as the outcome. Predictors will include baseline skin cancer threat and control beliefs, skin cancer risk factors, and demographics. These findings will be used in future studies to develop messages for groups that receive average risk feedback, which accounts for large segments of those tested for moderate risk susceptibility factors across many diseases.

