All subjects who participate in PGT-SC genetic testing will receive a telephone call two weeks after results are mailed, to assess PGT-SC result comprehension and potential distress (see Two Week Risk Feedback Comprehension Assessment) and to answer any questions they may have. All those who

complete this Assessment will receive a \$5 Target Gift card as thanks for their effort. Based on prior literature documenting low levels of distress in those undergoing genetic testing for high-risk mutations, and among those found to carry *CDKN2A* mutations, we anticipate low levels of distress regarding PGT-SC feedback. Anyone who reports high distress will be referred to Clinic Director and Co-Investigator [name], who addresses distress issues regularly in the UNM clinic. If they wish, a genetic counselor will be available.

E) Three-month follow-up.

All participants who completed Baseline Assessments (whether tested or not) will be contacted for assessment by telephone three months after PGT-SC testing (Three Month Follow Up Questionnaire). Participants who complete this three-month follow up assessment will receive a \$15 Target Gift card for their valued study participation.

F) Group 1 genetic testing option.

Those 120 participants randomized to the control group will receive an offer for PGT-SC directly after the three-month follow-up assessments. They will be offered testing, and of those who pursue testing, will receive results by mail or by email, sent by the PA who enrolled them, and a two-week follow-up telephone call to assess result comprehension and potential distress.

G) Summary.

We anticipate that patients will be enrolled over an approximately 12 month period, complete assessments and receive feedback within 20 months. Thus individuals are estimated to be in the study for 3 months and the enrollment and assessment period overall will last as long as 20 months total. Primary analyses will be completed in the 6 months following the 24 months period of participation; the entire study will take 3 years.

9) Study Endpoints.

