Primary endpoints are based on the 3-month follow up questionnaires. The primary study endpoints include personal utility of Personal Genomic Testing for Skin Cancer (PGT-SC) in terms of short-term (three months after testing) sun protection, skin screening (i.e., behaviors), communication, melanoma threat and control beliefs (i.e., putative mediators of behavior change), as well as differential reach of PGT-SC across Hispanics and non-Hispanics, as well as potential explanations for any differential reach. These will include the construct/measures listed below:

Construct/Measure	Prior work/psychometrics	Assess point
Sun protection and skin screening (Sunscreen, shade seeking, clothing and hat usage) on separate 5-point scales (never-always); health provider screening (no/yes).	Item reliability $\geq 80\%$. (Ganz, 2008)	B, 3-month
Family/physician communication. Frequency, content of communication with physicians, family, and friends regarding skin cancer risk, interest in genetic information; 4-point scales (not at all-a lot).	Items used with high comprehensibility in population-based studies ([name] 2005, 2009, 2012, 2014)	B, 3-month, (interest in genetic information only)

Perceived skin cancer threat belief (Witte 1996). Includes assessment of risk perceptions (verbal, percent likelihood, comparison) on separate scales (5 to 10-point) from low-high, with “don’t know” option (Waters 2013); worry, assessed with 4-point items (never-all the time). Perceived skin cancer control beliefs (Witte 1996) Includes skin cancer prevention self-efficacy (7 items, on separate 4-point scales; not at all-extremely capable), skin cancer prevention response-efficacy (7 items, on separate 4-point scales; not at all to extremely important).
	
Widely used perceived risk items drawn from prior health behavior research (Weinstein 1982), Lerman’s cancer worry scale (Lerman 1991), and perceived cancer severity (Aiken 1994). Control belief items (Bandura 1986) predicting uptake of cancer prevention behaviors; adapted for skin cancer prevention ([name] 2006).
	
B, 3-month (risk perception question only)

Hispanic ethnicity
	
For initial sampling frame (50%) Hispanic, self-report as per Baseline survey.
	
B

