Test result comprehension includes recall, perceived clarity, interpretation and recall, believability, and test regret on closed, open-ended scales.	Adopted from the NHGRI Multiplex Study (Kaphingst 2012, McBride 2009).	Risk feedback comp. assessment
Cancer-related Distress is assessed through 7 items on separate 5-point scales (not at all-extremely).	Impact of Events Scale – Revised Intrusive thoughts subscale (Horowitz 1979) is widely used with good internal and test-retest reliability; good ability to distinguish those with cancer distress (Joseph 2000; Thewes 2001).	Risk feedback comp. assessment; 3-month
Demographics (birth year, US nativity, survey language choice, gender, education, income, race/ethnicity); Internet availability.	Standard demographic questions; Internet availability (Nelson 2004).	B
Melanoma risk factors (personal and family melanoma history; phenotype, sunburn hx).	Heavily used items from prior epidemiology research (Gandini 2005).	B

References for Endpoints:

Bandura A. *Social foundations of thought and action: a social cognitive theory*. Englewood Cliffs, NJ: Prentice-Hall; 1986.

Espinosa de Los Monteros K, Gallo LC. The relevance of fatalism in the study of Latinas' cancer screening behavior: a systematic review of the literature. *International journal of behavioral medicine*. Dec 2011;18(4):310-318.

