Overall data processing and missing data imputation. We will first examine aspects of data quality and distributional assumptions to ensure statistical integrity and accuracy: 1) data skewness, kurtosis, and parametric assumptions; 2) intention-to-treat (ITT) principles; 3) missing data considerations; and 4) control of potentially inflated Type-I errors due to multiple statistical tests. First, data skewness and kurtosis will be examined to determine whether each variable significantly deviates from normality. If so, we will employ data transformations by taking a log or square root of the skewed variables, or by using the Box-Cox transformation or kernel estimation techniques (Diggle et al., 2002) to determine the best-fitting parametric density. Second, we assume that up to 20% of the respondents will be unreachable at our three-month follow-up assessment; missing assessments may be amenable to imputation by several powerful techniques that can handle both continuous and categorical data (Graham et al., 2997; Schafer and Olsen, 1998). A related approach is the use of Hierarchical Linear Models (HLM) (Raudenbush and Bryk, 2002) to use all available behavioral outcomes data since HLM does not carry out list-wise deletion by default, thus the statistical power loss due to missing data may be minimal. We will apply the intention-to-treat (ITT) principle (Nich and Carroll, 1997). An ITT analysis in Aim I (Nich and Carroll, 1997; Willett et al., 1998) would assume missing data is related to lack of sun protection adherence. We may use the Pattern-Mixture Model to examine whether or not missed follow-up assessments are associated with baseline characteristics with safeguards to minimize

model overfit (Hedeker and Gibbons, 1997). Finally, to control for potentially inflated type-I error rate due to multiple comparisons, analyses can also incorporate a multiple comparisons method, such as a False Discovery Rate-controlling procedure, which is more powerful than simple Bonferroni corrections.

References for Data Processing

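### Control beliefs and communication are named as primary three-month outcomes, but the measures table schedules no control-belief items and little of communication at three months

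*Combined protocol and SAP*

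**What the plan says.** Section 3, Aim I, sets the outcomes as "short-term (three months after testing) sun protection, skin screening (i.e., behaviors), communication, melanoma threat and control beliefs". Its hypothesis is comparative: "we hypothesize that behaviors and putative mediators will be higher in those who test, compared to those who decline testing or wait-list controls".

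Section 9 opens with "Primary endpoints are based on the 3-month follow up questionnaires", repeats the same five domains as primary endpoints, and introduces the construct/measure table as the list of measures for them. The last column of that table gives the time points:

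- Sun protection and skin screening: baseline and three months, with no restriction.
- Family/physician communication (frequency, content, and interest in genetic information): "B, 3-month, (interest in genetic information only".
- Threat beliefs (risk perceptions, worry) and control beliefs (7 self-efficacy and 7 response-efficacy items), sharing one cell: "B, 3-month (risk perception question only".
- Cancer-related distress: "Risk feedback comp. assessment; 3-month".

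Section 8 C places the Baseline Questionnaire before randomization. Section 8 F says: "Those 120 participants randomized to the control group will receive an offer for PGT-SC directly after the three-month follow-up assessments".

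**The concern.** The endpoint text and the schedule that is meant to deliver it disagree within one section. A measure taken only at baseline, before randomization, cannot be a three-month outcome and cannot show whether the offer of testing moved a mediator.

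Control beliefs are one of the two belief constructs that Aim I puts forward as routes to behavior change under Protection Motivation Theory. If the table describes what is collected, a named primary endpoint has no outcome value in either arm, and communication is reduced to interest in genetic information.

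The gap could not be closed afterwards. Section 13 says "missing assessments may be amenable to imputation by several powerful techniques", but that deals with people who miss a call, not with items put to nobody. Re-contacting the wait-list group later would not recover an untested control value, because that group is offered testing straight after the three-month assessment.

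**Working it through.** The finding is a comparison of texts, and the plan has no figure of its own to reproduce. Setting the five Aim I domains against the Section 9 table:

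| Aim I domain | Components in the table | Scheduled at three months |
|---|---|---|
| Sun protection | sunscreen, shade, clothing, hat | all |
| Skin screening | health provider screening | all |
| Communication | frequency, content, interest in genetic information | interest only (natural reading) |
| Threat beliefs | risk perceptions, worry | risk perceptions only |
| Control beliefs | 7 + 7 = 14 items | 0 of 14 |

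**Is the restrictive reading right?** Three things support it.

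1. The word 'only' restricts, and it appears in both cells. The sun protection cell has no such limit, and the distress cell adds a three-month point where one is intended. The column therefore marks three-month measures where they are planned.
2. No self-efficacy or response-efficacy item is a risk perception question, so none falls inside the exception in the shared cell.
3. No other part of the protocol schedules the omitted items at three months. The 7 distress items asked then are a different construct and do not stand in for worry.

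**How many participants are affected?** Section 13 assumes up to 20% unreachable at three months. Arm sizes are from Section 6.

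- Wait-list: 120 × 0.8 = 96
- PGT-SC: 530 × 0.8 = 424
- Total: 96 + 424 = 520 of 650

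At least 520 people would complete the call, and none would have a three-month control-belief score.

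**Would the comparison be informative if the items were asked?** The inputs are a two-sided alpha of 0.05 and 80% power. Both are assumptions, as the documents give neither for this outcome. The detectable standardized difference is approximately d = (1.960 + 0.842) × √(1/n₁ + 1/n₂).

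- Randomized arms after 20% loss: 2.802 × √(1/96 + 1/424) = 0.317 SD
- Randomized arms, no loss: 2.802 × √(1/120 + 1/530) = 0.283 SD (0.284 with the t-distribution)

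The Aim I hypothesis is framed around those who test, which is a smaller group. Section 6 expects 30 to 50 percent to accept testing. With 20% loss that is 530 × 0.30 × 0.8 ≈ 127 to 530 × 0.50 × 0.8 = 212 testers. Against 96 wait-list controls, the detectable difference is about 0.38 SD (127 testers) to 0.35 SD (212 testers). If fewer of those who accept return a sample, it is larger. The conflict itself does not depend on any of these figures.

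**The case against.** The strongest objection is that the Three Month Follow Up Questionnaire is named but not supplied. If it contains the items, the defect is a wrong table entry and nothing is lost from Aim I. This stands as a limit on the consequence, which is conditional on the schedule being followed. It does not remove the conflict.

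A second objection is that threat and control beliefs are separate constructs in one cell, and risk perception belongs to threat alone. The restriction might then apply only to threat, leaving control beliefs at both time points. Table layout may also have suffered in conversion from PDF. This reading is possible but strained, because 'only' qualifies the single three-month entry that serves the whole cell.

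Third, the communication cell has a comma before its parenthesis, so the reach of the restriction is less clear there. Interest in genetic information is also listed within that construct, so some measurement remains. Both points are fair: control beliefs are the firm part of the finding and communication the probable part.

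Fourth, the repeated 'only' may reflect a deliberate decision to shorten the call. The documents give no reason. If so, narrowing the endpoints removes the contradiction as well as adding items would, and the fix allows for that. It is also right that the 0.32 SD figure compares randomized arms, not testers with controls. It is given only to show that the outcome would be usable.

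**Conclusion.** The concern holds. The plan names communication, threat and control beliefs as primary three-month outcomes, while its own schedule limits what is asked of them at three months.

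As written, sun protection and screening are covered in full, and threat in part (no worry). Communication, on the natural reading, is covered only through interest in genetic information. Control beliefs are not covered at all: 0 of 14 items. The control-belief part of the Aim I hypothesis, and probably the frequency and content of communication, could not then be tested.

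This rests on the table reflecting the questionnaire, which the documents cannot confirm. The correction is needed in either case, because the protocol currently says that named primary outcomes are not collected. Sun protection, screening, risk perception, Aim Ia (which uses baseline beliefs as predictors), Aim II and Aim III are unaffected.

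**What to change.** Compare the Three Month Follow Up Questionnaire with the Section 9 table, then take one of three routes.

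1. **Items already in the questionnaire.** Correct the two time-point entries to baseline and three months without restriction. The cost is a table correction.
2. **Items absent and can be added.** Add the 14 control-belief items and the communication frequency and content items to the three-month call in both arms. Add worry as well if threat is to be analysed as the full construct. Amend the table to match. If calls have begun, make the change on the same date in both arms, record that date, and analyse these outcomes only in participants called after it. The cost is an IRB amendment and a longer call, whose present length the documents do not give. The items already exist at baseline, and the call is already planned and compensated. If calls have begun, fewer participants contribute and power falls below that implied by the 0.32 SD figure.
3. **Items cannot be added.** Before outcome data are analysed, restate Aim I and the Section 9 primary endpoints to cover only what is measured at three months: sun protection, screening, risk perception and interest in genetic information. Report the change. No new data collection is needed, but the control-belief and communication parts of Aim I are given up, and a change to primary endpoints has to be disclosed.

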Cognitive interviews to ensure high comprehensibility and acceptability of the translations will be conducted by [name] and [name].

The Department of Psychiatry & Behavioral Sciences at MSKCC will conduct data analysis on de-identified data.

11) Study Methods

*The timeline above gives very detailed information about study methods.

Subjects will be approached at their Clinic and asked if they are interested in participating. Individuals accompanying Clinic patients and who attend another UNM Clinic are eligible to participate.

They will then discuss the study with the bilingual interviewer and, if they are eligible agree and sign informed consent. All baseline surveys will then be completed with the PA in the clinic.

Identifiers will be collected and remain at UNM for mailing and follow-up. Subjects will then be de-identified at the end of the study (after 3 years).

Subjects will receive compensation for participation. ALL consented subjects will receive a \$15 Target Gift card after completion of the Baseline Questionnaire; those in the randomized to the wait list control Group 1 will receive compensation for the baseline survey and the three-month survey. Those randomized to Group 2, the PGT-SC arm will then be given information modules through the internet (or on paper if they prefer). They will be asked if they would like to participate in genetic testing for MC1R. Those randomized to receive PGT-SC who complete the online educational modules will be compensated \$5 Target Gift card per educational module, with a maximum of \$15 possible.

Additionally, among those who elect genetic testing, we will assess distress levels two weeks after the PGT -SC genetic results have been received, and will compensate participants for their time with a \$5 target Gift card. All participants who completed Baseline Assessments (whether tested or not) will be contacted for the final assessment by telephone approximately three months after recruitment.

Participants who complete the three-month outcome assessment will receive a \$15 Target Gift card. This level of compensation is reasonable for the level of effort required for subjects.

12) Data and Specimen Banking

For participants who indicate that they want to participate in genetic testing, we will mail saliva collection kits. They will give a sample of saliva and mail these back to the study in pre-addressed, stamped envelopes. These will be delivered to the UNM Molecular Epidemiology Laboratory at UNM HSC. DNA will be extracted and sequenced for MC1R only, a gene that is important for pigmentation. Specimens will be destroyed when a good test result is obtained. Data will be kept until the end of the study when it will be destroyed. [name], the Manager of the Molecular Epidemiology Laboratory, will be the only person with access to the specimens. Each specimen will have a separate ID number that links it to the donor. When the specimen has been assayed, the de-identified information will then be given to the study team ([name], [name], data analyst) and to the donor.

No information, other than participant study number, will be stored with the specimen. Results will be identifiable to authorized personal at UNM (PAs, [name] and [name]) until the end of the study. Genetic testing will be done for MC1R only by sending the DNA from the participants to an outside accredited laboratory but will be completely de-identified.

SOMBRA Protocol for DNA Extraction

Important Points before starting:

- Perform all centrifugation steps at room temp (15-25°C)
- Preheat the water bath at 56°C.
- If Buffer AL or Buffer ATL contains precipitates, dissolve by heating to 70°C with gentle agitation.
- Make sure Buffer AW1 and Buffer AW2 are prepared (follow specified instructions) before purification steps are initiated.

Day 1:

1. Add 500 μ l of 100% ethanol to each sample and mix by inversion (or vortexing) for one minute. The tissue will now appear chalky white.
2. Centrifuge the samples at 12,000 rpm for 5 minutes at room temperature and remove the supernatant.
3. Repeat step 1 and 2 once for a total of two ethanol washes.
4. Dry the tissue pellet by inversion under the hood until the ethanol is evaporated. This may take anywhere from 25-60 minutes depending on pellet size. At this point the pellet can be frozen at -80C or proceed with the next step.
5. To the pellet, add 120 μ l of Buffer ATL, and 20 μ l Proteinase K (QIAGEN; 20 μ g/ μ l stock). Mix thoroughly by pulse-vortexing for 15 sec. (note: begin this step in the morning)
6. Place the 1.5 ml tube in a water bath and incubate at 56°C. Pulse vortex for 15 seconds every hour. Incubate samples at 56°C overnight.

Day 2:

1. Add 60 μ l of Buffer ATL, and 10 μ l Proteinase K to the sample in the morning and continue to incubate at 56°C. Pulse vortex for 15 seconds every hour and then continue incubation overnight.

Day 3:

Before starting:

- Warm AE Buffer to 37°C.
- Chill 100% ethanol on ice.
- Make labels for 2mL collection tubes and non-siliconized 1.5mL microfuge tube for each sample.

1. Add 200 μ l Buffer AL, close the lid and mix by pulse-vortexing for 15 s. If a precipitate forms, incubate samples at 56°C for 10 min. Following this step allow the samples to cool to RT (~10 min). Do not place these samples on ice, or the precipitate will form again. While the samples are cooling, place 100% on ice to prepare for the next step.
2. Add 200 μ l ice-cooled ethanol (100%), close the lid and mix by pulse-vortexing for 15 sec.

- Incubate at room temperature for 5 min.
3. Pulse centrifuge the 1.5 ml tube to remove drops from the inside of the lid.
 4. Carefully transfer the entire lysate from step 3 to the QIAamp MinElute column without wetting the rim. Centrifuge at 6000 x g (8000 rpm) for 1 min. (If the lysate has not completely passed through the membrane after centrifugation, centrifuge again until the column is empty.)
 5. Place the MinElute column in a clean 2 ml collection tube and discard the collection tube containing the flow through.
 6. Carefully add 500 μ l Buffer AW1. Centrifuge 6000 x g (8000 rpm) for 1 min.
 7. Place the MinElute column in a clean 2 ml collection tube and discard the collection tube containing the flow through.
 8. Carefully add 500 μ l Buffer AW2. Centrifuge 6000 x g (8000 rpm) for 1 min. (note: be careful when removing the tubes from the rotor, do not allow the flow through to contact the column during this step)
 9. Place the MinElute column in a clean 2 ml collection tube and discard the collection tube containing the flow through.
 10. Centrifuge at 20,800 x g (14,000 rpm) for 3 min to dry the membrane completely.
 11. Place the MinElute column in a clean 1.5 ml microcentrifuge tube and discard the collection tube containing the flow-through.
 12. Apply (to the center of the column; on the membrane) 20 μ l AE Buffer (warmed to 37°C). Close the lid and incubate at room temperature for 5 min.
 13. Centrifuge 20,800 x g (14,000 rpm) for 1 min.
 14. Repeat elution step (Step 12 and 13 above). Optional: repeat steps 12 and 13 multiple times.

SOMBRA Sequencing Protocol

Genotyping. MC1R will be sequenced using a 1125bp PCR-amplified fragment to cover the coding region. Information on primers and cycling parameters is listed in supplemental data.

Excess nucleotides and primers will be removed using shrimp alkaline phosphatase/exonuclease I using standard conditions.

The BigDye® terminator cycle sequencing followed under standard conditions using one of four primers to address the carboxy – terminus - , transmembrane - , and the amino – terminus regions. Products were sequenced on an ABI Prism 3700 (Applied Biosystems, Foster City, CA) and electropherograms will be read by an independent reviewer using the Sequencher software v.4.05 (Gene Codes Corporation, Ann Arbor, MI).

13) Data Management

Information Collected. We will identify each subject with a unique ID linked to PHI (name, address, telephone number, age, sex and ethnicity) which is only kept by the study team at UNM and overseen by [name]. These files will be stored in space belonging to [name] and maintained in a locked cabinet in a locked room in a secure building. This link will be destroyed at the end of the study, upon completion of data analysis. **Only UNM study personnel will have access to this PHI.** [name] has the responsibility for the transmission and receipt of any data.

Overall data processing and missing data imputation. We will first examine aspects of data quality and distributional assumptions to ensure statistical integrity and accuracy: 1) data skewness, kurtosis, and parametric assumptions; 2) intention-to-treat (ITT) principles; 3) missing data considerations; and 4) control of potentially inflated Type-I errors due to multiple statistical tests. First, data skewness and kurtosis will be examined to determine whether each variable significantly deviates from normality. If so, we will employ data transformations by taking a log or square root of the skewed variables, or by using the Box-Cox transformation or kernel estimation techniques (Diggle et al., 2002) to determine the best-fitting parametric density. Second, we assume that up to 20% of the respondents will be unreachable at our three-month follow-up assessment; missing assessments may be amenable to imputation by several powerful techniques that can handle both continuous and categorical data (Graham et al., 2997; Schafer and Olsen, 1998). A related approach is the use of Hierarchical Linear Models (HLM) (Raudenbush and Bryk, 2002) to use all available behavioral outcomes data since HLM does not carry out list-wise deletion by default, thus the statistical power loss due to missing data may be minimal. We will apply the intention-to-treat (ITT) principle (Nich and Carroll, 1997). An ITT analysis in Aim I (Nich and Carroll, 1997; Willett et al., 1998) would assume missing data is related to lack of sun protection adherence. We may use the Pattern-Mixture Model to examine whether or not missed follow-up assessments are associated with baseline characteristics with safeguards to minimize

model overfit (Hedeker and Gibbons, 1997). Finally, to control for potentially inflated type-I error rate due to multiple comparisons, analyses can also incorporate a multiple comparisons method, such as a False Discovery Rate-controlling procedure, which is more powerful than simple Bonferroni corrections.

References for Data Processing

